6.1.2. Dose Modifications Due to Hematologic Toxicity

It is not expected that the dose will need to be held or modified due to hematologic toxicity in this study. If a Grade 1 or 2 hematologic toxicity does occur, hold orteronel and re-evaluate the patient in 1 week. Absolute neutrophil count and platelets should be monitored weekly until recovery. If ANC and/or platelets do not recover within 3 weeks to \leq Grade 1, the patient will be discontinued from the study.

6.1.3. Dose Modifications Due to Non-Hematologic Toxicity

Due to its mechanism of action, treatment with orteronel may elicit expression of adverse reactions typically associated with androgen deprivation. Risks associated with androgen deprivation include hot flushes, decreased libido, loss of energy, QTc interval prolongation, or mood swings. Long-term effects of testosterone suppression may also occur, including effects on bone mineral density, muscle mass, hyperglycemia, or lipid or energy metabolism.

Adverse events commonly recorded during clinical trials with orteronel include fatigue, nausea and vomiting, rash, and worsening hypertension. Pancreatitis and/or elevated amylase/lipase have also been reported, occurring in <5% of patients in studies conducted with orteronel.

CONFIDENTIAL

STUDY DRUG: Orteronel

SCRI INNOVATIONS STUDY NUMBER: BRE 203

DATE OF PROTOCOL: Version 3.0 30 October 2013

Pancreatic enzymes will be measured during scheduled serum chemistries for patients receiving long-term administration of orteronel.

For fatigue, mild or intermittent nausea and vomiting, or rash, dose modifications of orteronel should follow the guidelines in Section 6.1.1, depending on the severity.

For \geq Grade 3 QTc interval prolongation (QTcF >500 ms or >60 ms change from baseline on at least two separate ECGs), orteronel should be held until recovery to \leq Grade 1 (<480 ms). The patient's chemistries should be checked, as well as concomitant medication usage. Once QTc interval prolongation has resolved, orteronel may be restarted at the reduced dose level. For a second occurrence of \geq Grade 3 QTc interval prolongation, orteronel should be discontinued.

In the event of any grade 4 non-hematologic toxicity, orteronel should be discontinued.

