11. History of myocardial infarction, unstable symptomatic ischemic heart disease, ongoing arrhythmias $>$ Grade 2 (National Cancer Institute [NCI] Common Terminology Criteria for Adverse Events [CTCAE], Version 4.0), thromboembolic events (eg, deep vein thrombosis, pulmonary embolism, or symptomatic cerebrovascular events), or any other cardiac condition (eg, pericardial effusion restrictive cardiomyopathy) within 6 months prior to first dose of study drug. Chronic stable atrial fibrillation on stable anticoagulant therapy is allowed.
12. New York Heart Association (NYHA) Class III or IV heart failure (Appendix B)

CONFIDENTIAL

STUDY DRUG: Orteronel

SCRI INNOVATIONS STUDY NUMBER: BRE 203

DATE OF PROTOCOL: Version 3.0 30 October 2013

13. Electrocardiogram (ECG) abnormalities of:
 - Q-wave infarction, unless identified 6 or more months prior to screening
 - QTc Fridericia (F) interval > 460 msec
14. Inadequately controlled hypertension (ie, systolic blood pressure [SBP] >160 mmHg or diastolic BP [DBP] >90 mmHg) at 2 separate measurements no more than 60 minutes apart during the Screening visit. Note: patients may be rescreened after adjustment of antihypertensive medications.
15. Known diagnosis of human immunodeficiency virus, active chronic hepatitis B, or C, life-threatening illness unrelated to cancer, or any serious medical or psychiatric illness that could, in the investigator's opinion, potentially interfere with participation in this study
16. Uncontrolled diabetes mellitus. Patients with Type II diabetes are eligible if they require only oral hypoglycemic agents and fasting blood glucose level is ≤ 120 . Patients with Type I diabetes are eligible if their glycosylated hemoglobin (HbA_{1c}) is ≤ 7 .
17. Diagnosis or treatment for another malignancy within 2 years of enrollment, with the exception of adequately treated in-situ carcinoma of the cervix, uteri, basal or squamous cell carcinoma or non-melanomatous skin cancer
18. Inability or unwillingness (including psychological, familial, sociological, or geographical conditions) to comply with study and/or follow-up procedures as outlined in the protocol.
19. Use of a prohibited concomitant medication (see Section 5.3.2 and Appendix D) that cannot be safely discontinued or substituted.

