5. STUDY DESIGN

This is an open-label, multicenter, Phase II study to be conducted in 2 stages. All patients will receive orteronel PO at a dose of 300 mg twice daily (BID) (600 mg total daily dose).

- Lead-in Phase: The first 6 patients treated will be evaluated every week to confirm the safety and feasibility of this regimen. After all 6 patients complete at least 4 weeks of treatment, and if no prohibitive toxicities are identified, continuous study treatment will begin.
- Continuous Study Treatment: Patients will continue to be enrolled into both cohorts based on their tumor specificities up to a total of 31 patients in Cohort 1 (ER-/PR-/HER2-/AR+) and 55 patients in Cohort 2 (ER+ and/or PR+/AR+). These numbers include the patients that are participating in the lead-in phase.

Up to 86 patients are planned to be enrolled in this study (6 for the lead-in phase and 80 for continuous study treatment).

Patients will be evaluated every eight weeks for response to treatment.

All patients who respond to treatment (complete response [CR] or partial response [PR]) or have stable disease (SD) will continue to receive orteronel until they develop progressive disease (PD) or unacceptable toxicity.

The study design schema is presented in Figure 1.

[figure not shown]
CONFIDENTIAL

STUDY DRUG: Orteronel

SCRI INNOVATIONS STUDY NUMBER: BRE 203

DATE OF PROTOCOL: Version 3.0 30 October 2013

Figure 1. BRE 203 Treatment Schema

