Appendix E: Schedule of Assessments for BRE 203 (continued)

- ^a Physical examinations will include measurements of vital signs (resting heart rate, blood pressure, respiratory rate, oral temperature). At the baseline visit only, height will also be recorded and weight will be recorded only on Day 1 of each cycle.
- ^b Hematological parameters include the following laboratory tests: complete blood count consisting of red blood cell count (RBCs), hemoglobin, total white blood count (WBC) with differential, and platelet count. Do not repeat on C1D1, if baseline within 72 hours.
- ^c CMP assessment includes the following laboratory tests: glucose, BUN, creatinine, sodium, potassium, chloride, calcium, CO₂, alkaline phosphatase (ALP), AST, ALT, total bilirubin, total protein, and albumin. Do not repeat on C1D1, if baseline within 72 hours.
- ^d Fasting plasma glucose, insulin, and c-peptide will be drawn at screening, predose on Day 1 of odd-numbered cycles (Cycles 3, 5, 7, etc), and at study completion for patients with a history of diabetes.
- ^e A single ECG will be obtained at baseline for QTcF interval assessment for all patients. A single ECG will also be obtained predose on Cycle 3 Day 1 and then every 2nd cycle (Cycles 5, 7, 9, etc).
- ^f Archived tumor tissue from a primary biopsy or metastatic lesion is required for centralized testing of AR expression. Patients with AR expression $\geq 10\%$ will be screened for enrollment into the study. Additional tumor tissue, if available from the patients enrolled on study, will be retained to perform correlative testing (15 to 20, 4 um unstained slides). Patients may enroll based on local laboratory AR assessment, but will need to submit tissue for confirmation at the central laboratory.
- ^g Informed consent must be obtained ≤ 28 days prior to the initiation of trial treatment. The physical examination, ECOG performance status, serum/urine pregnancy test (for women of child-bearing potential only), and complete blood counts (CBCs) should be done ≤ 7 days prior to initiation of treatment.
- ^h If clinically indicated.
- ⁱ Day 1 of each cycle following Cycle 1
- ^j Serum hormone levels will be drawn at screening, on Day 1 of Cycles 2 and 4, and at the end of study visit.
- ^k Do not repeat on Cycle 1 Day 1, if baseline was done within 72 hours.
- ^l Lead-in patients only
- ^m If no documented progressive disease and the last assessment was >8 weeks prior. Only abnormal scans at baseline need to be repeated.

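### Section 6.1.3's QTc rule lets one reading both trigger the hold and count as recovery when baseline QTcF is below 420 ms, and the confirming ECG is not timed

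*Combined protocol and SAP*

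**What the plan says.** Section 6.1.3 lists QTc prolongation among the risks of androgen deprivation and gives it its own rule. An event of Grade 3 or worse is defined and acted on in one sentence: "QTcF >500 ms or >60 ms change from baseline on at least two separate ECGs), orteronel should be held until recovery to" a state at or below "Grade 1 (<480 ms"). The text continues: "Once QTc interval prolongation has resolved, orteronel may be restarted at the reduced dose level". A second occurrence of Grade 3 or worse means discontinuation.

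Four other places bear on how the rule works:

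- **Section 3.2, item 13** excludes patients with "QTc Fridericia (F) interval > 460 msec". It sets no lower bound.
- **Appendix E, footnote e** fixes the reference value: "A single ECG will be obtained at baseline for QTcF interval assessment for all patients". It then sets the on-treatment readings: "A single ECG will also be obtained predose on Cycle 3 Day 1 and then every 2nd cycle (Cycles 5, 7, 9, etc"). Section 7.4.2 gives the same schedule.
- **Section 6.1.1.1** has a general Grade 3 rule for events at least possibly related to the drug. It sets a two-week minimum hold, reassessment at least every two weeks after the dose has been lowered, and discontinuation when a treatment-related delay exceeds three weeks, unless the physician and the Medical Monitor or Study Chair agree otherwise.
- **Section 6.1** lets the treating physician hold or reduce the dose when clinically indicated.

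**The concern.** A hold rule needs an entry condition and an exit condition that cannot both be true of the same patient on the same reading. Here the entry condition has two limbs, one absolute and one measured from baseline, while the stated exit is absolute only. A patient who enters by the relative limb may already satisfy the exit.

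The choice of reading affects whether the patient is held, when a restart is allowed, and whether a persisting prolongation counts as one event or two. The last matters most, because the second occurrence ends treatment. Two sites with identical tracings could therefore act differently, and those differences would carry into the dose, duration and dose-intensity summaries planned in Section 10.7.

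A second problem concerns timing. The definition calls for more than one ECG, but the schedule supplies one reading every second cycle, and nothing says when a confirming or a recovery ECG is to be taken.

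**Working it through.** The plan gives no figure of its own on this point to reproduce. The check is a comparison of conditions plus calendar arithmetic. Write b for baseline QTcF and q for an on-treatment QTcF, both in ms.

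**Inputs.** Trigger: q > 500, or q − b > 60 (Section 6.1.3). Recovery: q < 480 (Section 6.1.3). Entry: b ≤ 460 (Section 3.2). Cycle: 28 days, ±5 days (Section 7.4). ECGs: Day 1 of Cycles 3, 5, 7 and so on (Section 7.4.2; Appendix E, footnote e).

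**Step 1, relative limb against recovery.** Both hold when b + 60 < q < 480. Such a q exists only if b + 60 < 480, that is b < 420. In whole milliseconds q runs from b + 61 to 479, so the largest baseline with an overlap is 418.

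| Baseline b | Readings that both trigger and meet recovery |
|---|---|
| 380 | 441–479 |
| 400 | 461–479 |
| 405 | 466–479 |
| 410 | 471–479 |
| 418 | 479 |
| 419–460 | none |

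**Step 2, absolute limb against recovery.** No q is both above 500 and below 480, so this limb does not overlap.

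**Step 3, following one patient through.** Baseline 405, two readings of 470. The change is 470 − 405 = 65 > 60, so the event is Grade 3 or worse and dosing is held. Also 470 < 480, so the stated recovery limit is met. If that limit is taken at face value, restart at the reduced level is open. A later pair of readings, still at 470, is again +65 and meets the trigger again. The text does not say what separates one occurrence from the next, so the same unresolved prolongation can be recorded as the second and lead to discontinuation.

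**Step 4, schedule.** Day 1 of Cycle c is study day 1 + 28(c − 1). Cycle 3 gives Day 57 and Cycle 5 gives Day 113; 113 − 57 = 56 days, or 8 weeks. One ±5-day shift makes this 51 to 61 days; a shift in each of the two cycles makes it 46 to 66 days. This is the interval to the next scheduled ECG, not a wait that the text imposes.

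**Step 5, does Section 6.1.1.1 close the gap?** If it applies, dosing stops for at least 14 days, but recovery is still defined as q < 480. Its reassessment clause begins only after a dose reduction and does not mention an ECG. Its three-week limit on delay (21 days) is shorter than the 56 days to the next scheduled ECG, so a recovery reading within that limit would have to be unscheduled. Section 6.1.3 sends fatigue, mild nausea and vomiting, and rash to Section 6.1.1 but writes out a separate rule for QTc. Section 6.1.1.1, for its part, says only that renal and liver modifications are presented separately. Whether it governs QTc events is therefore open.

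**The case against.** The strongest defence is that Section 6.1.3 should be read as a whole. It requires return to Grade 1 or better and permits restart only after the prolongation has resolved. By its own definition a patient still more than 60 ms above baseline is Grade 3 or worse, so has not recovered. On that reading the 480 ms figure is incomplete shorthand and no one is restarted early. This is a sensible way for an investigator to act. But the only numeric meaning the text gives to Grade 1 or better is below 480 ms, so both readings are available and the text does not choose between them.

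A reader might infer that the hold ends the moment it begins. That goes too far. The two-week minimum in Section 6.1.1.1 may apply, and if it does, restart is delayed. It would not mend the recovery definition.

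A reader might also infer that the rule contradicts the ECG schedule, so that a site must keep dosing for eight weeks after a prolonged reading. The documents do not support this. Section 7.4.2 and Appendix E list planned ECGs and bar no others, Section 6.1.3 does not require the two ECGs to be scheduled ones, and Section 6.1 allows a clinically indicated hold at any time. If the two-ECG condition qualifies only the relative limb, one reading above 500 ms triggers the hold by itself. What remains is a silence: no passage times the confirming or recovery ECG, and the scope of the two-ECG condition is ambiguous.

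**Conclusion.** The point stands in limited form and should be fixed. For every baseline QTcF below 420 ms, the change-from-baseline trigger and the stated recovery limit can be met by the same reading. The overlap needs no assumption beyond the thresholds printed in Section 6.1.3, and entry up to 460 ms does not exclude such baselines. It does not touch the limb above 500 ms or baselines of 420 ms and over. The missing timing for confirming and recovery ECGs is a related gap, with 56 days as the nominal distance between scheduled readings.

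The number of patients affected cannot be given. The documents contain neither a distribution of baseline QTcF nor an incidence of rises above 60 ms. The share of patients below 420 ms, even if it were known, would not be the share affected. Nor do the documents show that adverse-event severity counts would shift, since Section 10.7 grades by CTCAE.

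A reader might further infer that the lead-in decision is taken with no on-treatment ECG data. The documents support only that none is required beforehand. The decision waits until all six patients have completed at least four weeks, so with staggered entry a patient who started 28 or more days before the sixth could have reached Cycle 3 Day 1 (Day 57) by then.

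**What to change.** The sponsor should reconcile Sections 6.1.1.1, 6.1.3 and 7.4.2 and Appendix E, footnote e, so that:

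- no patient can meet the hold trigger and the recovery definition on the same reading, and it is clear when a persisting prolongation counts as a second occurrence;
- the text says whether the two-ECG condition covers both trigger limbs or only the change from baseline;
- the text says how that condition and the recovery check relate to the ECG schedule;
- the text says whether the general Grade 3 rule in Section 6.1.1.1 applies to QTc events.

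All clinical thresholds, ECG timing and dosing rules are for the sponsor to set; none is proposed here. The cost is a wording amendment, with no effect on sample size or the primary analysis.

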6.1.3.1. Fatigue

Fatigue is defined as a disorder characterized by a state of generalized weakness with a pronounced inability to summon sufficient energy to accomplish daily activities.

Grade 2 to Grade 3 fatigue has occurred in some patients receiving TAK 700 without concomitant prednisone. Less severe Grade 1 or Grade 2 fatigue has been reported in some men receiving concomitant prednisone; other factors such as acute androgen deprivation may also be contributing to symptoms. Table 2 presents the CTCAE Criteria (Version 4.0) for fatigue and the appropriate actions to be followed.

Table 2 CTCAE Criteria and Appropriate Actions for Fatigue

CTCAE Grade	Event Definition	Action Required
1	Fatigue relieved by rest	No action required
2	Fatigue not relieved by rest, limits instrumental Activity of Daily Living (ADL)	Dose modification is optional; If Grade 2 fatigue is intolerable, dose reduction and re-escalation should follow guidelines in Section 6.1.1.2.
3	Fatigue not relieved by rest, limiting self care ADL	Dose reduction follows guidelines in Section 6.1.1.1.

Source: CTCAE Version 4.0

Abbreviations: ADL = activity of daily living

6.1.3.2. Gastrointestinal Adverse Events

Nausea

Nausea is defined as a disorder characterized by a queasy sensation and/or the urge to vomit. Table 3 summarizes the CTCAE Criteria (Version 4.0) for nausea and the appropriate actions to be followed.

CONFIDENTIAL

STUDY DRUG: Orteronel

SCRI INNOVATIONS STUDY NUMBER: BRE 203

DATE OF PROTOCOL: Version 3.0 30 October 2013

Table 3 **CTCAE Criteria and Appropriate Actions for Nausea**

CTCAE Grade	Event Definition	Action Required
1	Loss of appetite without alteration in eating habits	No action required
2	Oral intake decreased without significant weight loss, dehydration, or malnutrition	Concomitant anti-emetics may initially be administered without dose reduction. If Grade 2 nausea persists and is intolerable, dose reduction and re-escalation should follow Grade 2 Dose Reduction and Dose Re-escalation guidelines
3	Inadequate oral caloric or fluid intake; tube feeding, TPN, or hospitalization indicated	Supportive care regimen should follow local standard of care. Follow Dose Reduction and Dose Re-escalation guidelines

Source: NCI CTCAE Version 4.0

Abbreviation: CTCAE = Common Terminology Criteria for Adverse Events; TPN = total parenteral nutrition

Vomiting

Vomiting is defined as a disorder characterized by the reflexive act of ejecting the contents of the stomach through the mouth. Table 4 summarizes the CTCAE Criteria (Version 4.0) for vomiting and the appropriate actions to be followed.

Table 4 **CTCAE Criteria and Appropriate Actions for Vomiting**

CTCAE Grade	Event Definition	Action Required
1	Vomiting 1 to 2 episodes (separated by 5 minutes) in a 24-hour period	No action required
2	Vomiting 3 to 5 episodes (separated by 5 minutes) in a 24-hour period	Concomitant anti-emetics may initially be administered without dose reduction. If Grade 2 vomiting persists and is intolerable, dose reduction should follow Grade 2 Dose Reduction and Dose Re-escalation guidelines
3	Vomiting \geq 6 episodes (separated by 5 minutes) in a 24-hour period; tube feeding, TPN, or hospitalization indicated	Dose reduction follows Grade 3 Dose Reduction and Dose Re-escalation guidelines
4	Life-threatening consequences; urgent intervention indicated	Discontinue orteronel

Source: CTCAE Version 4.0

Abbreviation: CTCAE = Common Terminology Criteria for Adverse Events; TPN = total parenteral nutrition

CONFIDENTIAL

STUDY DRUG: Orteronel

SCRI INNOVATIONS STUDY NUMBER: BRE 203

DATE OF PROTOCOL: Version 3.0 30 October 2013

Note: It is possible that nausea and vomiting could be secondary to acute adrenal insufficiency, e.g., caused by sudden cessation of prednisone dosing. If nausea and vomiting occur in the setting of severe fatigue, prostration, or hypotension, blood should be obtained to check the electrolytes. Institutional standard of care should be followed in the presence of electrolytes imbalance. Even if the vomiting occurs shortly following the study drug dose, no re-dosing of study drug will be done.

Diarrhea

Patients should be treated according to institutional standard of care. Fluid intake should be maintained to avoid dehydration.

Diarrhea is defined as a disorder characterized by frequent and watery bowel movements. Table 5 summarizes the CTCAE Criteria (Version 4.0) for diarrhea and the appropriate actions to be followed.

Table 5 **CTCAE Criteria and Appropriate Actions for Diarrhea**

CTCAE Grade	Event Definition	Action Required
1	Diarrhea increase of < 4 stools per day over baseline; mild increase in ostomy output compared to baseline	No action needed
2	Increase of 4 to 6 stools per day over baseline; moderate increase in ostomy output compared to baseline	Concomitant anti-diarrheal agents may initially be administered without dose reduction. If Grade 2 diarrhea persists, dose reduction should follow Grade 2 Dose Reduction and Dose Re-escalation guidelines Supportive care regimen should follow local standard of care
3	Increase of \geq 7 stools per day over baseline; incontinence ~ hospitalization indicated; severe increase in ostomy output compared to baseline; limiting self care ADL	Dose reduction follows Grade 3 Dose Reduction and Dose Re-escalation guidelines
4	Life-threatening consequences; urgent intervention indicated	Discontinue orteronel

Source: CTCAE Version 4.0

Abbreviation: CTCAE = Common Terminology Criteria for Adverse Events; TPN = total parenteral nutrition

6.1.3.3. Hyperglycemia

Androgen deprivation has been associated with the new onset of diabetes.

CONFIDENTIAL

STUDY DRUG: Orteronel

SCRI INNOVATIONS STUDY NUMBER: BRE 203

DATE OF PROTOCOL: Version 3.0 30 October 2013

If the patient has a medical history of diabetes mellitus (type I or type II), the patient's diabetes should be followed frequently per local standard of care. A physician experienced in the management of diabetes should be involved in the patient's care. Patients should be counseled for the importance of diet and compliance with diabetic treatment throughout the study; any change in symptoms or home glucose monitoring results should be reviewed at each scheduled visit, and the patient should be encouraged to follow up as required with the physician managing the patient's diabetes. The physician managing the patient's diabetes should be informed whether the patient is on or has recently started any prednisone therapy.

Changes in diabetic medication should be supervised by or be based on consultation with the physician managing the patient's diabetes.

At baseline, if the HbA_{1c} concentration is >7%, the patient should be referred for further assessment to ensure adequate or improved diabetes control while on study. During the study treatment, if there is an increase in HbA_{1c} of 1.5% above baseline or to >8.0%, the patient should be referred to the physician managing the patient's diabetes for additional management support. The management of hyperglycemia or diabetes should be addressed before considering study drug reduction or hold.

Worsening of diabetic control is often associated with acute or chronic infection, other acute illness, new medication (diuretics or beta blockers), or electrolyte abnormalities (hypokalemia). Assessment for these underlying precipitating factors should always be considered in addition to adjusting the diabetes treatment regimen.

Table 6 presents the guidelines that apply to either new onset or previously diagnosed diabetes.

CONFIDENTIAL

STUDY DRUG: Orteronel

SCRI INNOVATIONS STUDY NUMBER: BRE 203

DATE OF PROTOCOL: Version 3.0 30 October 2013

Table 6 **CTCAE Criteria and Appropriate Actions for Hyperglycemia**

Grade	Event Definition	Action Required
1	Fasting glucose value > 130 up to 160 mg/dL; Fasting glucose value > 6.0 up to 8.9 mmol/L	Review compliance with diabetic medications, check HbA1c. Refer the patient to a physician experienced with management of the diabetes if HbA1c is > 7.0%. No dose modification is required.
2	Fasting glucose value > 160-250 mg/dL; Fasting glucose value > 8.9-13.9 mmol/L	Check HbA1c. If > 7.0%, make sure that the patient is currently under care of a physician experienced with management of the diabetes and refer the patient to that physician for evaluation. Seek precipitating cause(s). Reassess after 2 weeks. No dose modification is required.
3	> 250-500 mg/dL; > 13.9-27.8 mmol/L; hospitalization indicated	Review and assure treatment of precipitating causes, including new infections or hypokalemia. If blood glucose does not improve to Grade \leq 2, hold orteronel for 2 weeks then reassess. Monitor patient for signs and symptoms of adrenal insufficiency. If the hyperglycemia event was precipitated by a well-defined intercurrent event, orteronel may be resumed at the same dose, if blood glucose improves to Grade \leq 2. Otherwise, orteronel should be resumed at the reduced dose (200 mg BID).
4	> 500 mg/dL; > 27.8 mmol/L; life-threatening consequences	Discontinue orteronel.

Source: CTCAE Version 4.0

Abbreviations: BID = twice daily; HbA_{1c} = glycosylated hemoglobin

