- ER+ and/or PR+ (*Note: This group of patients must have received at least 1 and up to 3 prior hormonal therapies and at least one prior chemotherapy treatment in the advanced setting. HER2+ patients in this group must have received a minimum of 2 lines of HER2-directed therapy in the advanced setting at least 1 trastuzumab-containing regimen for metastatic disease.*) This group of patients may be pre-menopausal with ovarian suppression or post-menopausal. LHRH agonists maybe used to render ovarian suppression with post-menopausal ranges of estradiol or FSH per institutional guidelines.

Section 3.2 Exclusion Criteria

19) ***Use of a prohibited concomitant medication (see Section 5.3.2 and Appendix D) that cannot be safely discontinued or substituted.***

Section 5.3.2 Prohibited Concomitant Medications

- Concomitant treatment with any medication that may cause QT prolongation or Torsades de Pointes (see Appendix D). If a patient, after study enrollment, requires use of a medication that may cause QT prolongation and/or Torsades de Pointes ***that cannot be safely substituted***, the patient must be removed from the study.

CONFIDENTIAL

STUDY DRUG: Orteronel

SCRI INNOVATIONS STUDY NUMBER: BRE 203

DATE OF PROTOCOL: Version 3.0 30 October 2013

BRE 203 CLINICAL PROTOCOL SYNOPSIS

Title of Study:	A Phase II Study with Orteronel as Monotherapy in Patients with Metastatic Breast Cancer (MBC) that Expresses the Androgen Receptor (AR)	
SCRI Innovations Protocol Number:	BRE 203	
Sponsor:	SCRI Development Innovations, LLC	
Study Duration:	The total duration of the study is planned to be 48 months (enrollment and active treatment).	Phase of Study: II
Study Centers:	This is a multicenter study to be conducted in the United States at approximately 15 sites.	
Patient Population	
This study will enroll patients with MBC who have progressed on prior hormonal/chemotherapy regimens and whose cancer expresses AR. Patients will be enrolled onto one of the 2 following cohorts based on their tumor specificity:
 
 • Cohort 1: Patients with estrogen receptor negative (ER-)/progesterone receptor negative (PR-)/ human epidermal growth factor receptor 2 negative (HER2-)/AR positive (+) MBC with 1 to 3 previous treatments for metastatic disease • Cohort 2: Postmenopausal women with ER+ and/or PR+/AR+ refractory MBC who have progressed after at least one, and up to 3, previous hormonal treatments for metastatic disease. 	

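### Table 6 prints two Grade 1 hyperglycemia lower limits that do not convert into each other: 130 mg/dL is 7.2 mmol/L, not 6.0

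*Combined protocol and SAP*

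**What the plan says.** Section 6.1.3.3 says that Table 6 covers both newly arising and known diabetes. The table gives each grade's glucose range in mg/dL and again in mmol/L:

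- Grade 1: "Fasting glucose value > 130 up to 160 mg/dL; Fasting glucose value > 6.0 up to 8.9 mmol/L"
- Grade 2: "Fasting glucose value > 160-250 mg/dL; Fasting glucose value > 8.9-13.9 mmol/L"
- Grade 3: "> 250-500 mg/dL; > 13.9-27.8 mmol/L; hospitalization indicated"
- Grade 4: "> 500 mg/dL; > 27.8 mmol/L; life-threatening consequences"

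The Grade 1 action begins "Review compliance with diabetic medications, check HbA1c" and goes on: "Refer the patient to a physician experienced with management of the diabetes if HbA1c is > 7.0%. No dose modification is required". Neither the table nor the surrounding text says which unit takes precedence when the two disagree.

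**The concern.** Two columns of limits in different units should describe the same boundaries. Here the lowest boundary differs by unit, so a single blood sample can be Grade 1 or ungraded depending on which figure the site reads. Table 6 also prescribes an action for each grade, so the disagreement decides whether the Grade 1 steps are triggered. At stake are consistent Grade 1 labelling and consistent early follow-up of raised glucose. Section 6.1.3.3 itself links androgen deprivation to new-onset diabetes.

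**Working it through.** **Inputs.** The four pairs of limits come from Table 6. The conversion factor is not in the documents. I use 18.016 mg/dL per mmol/L (molar mass of glucose about 180.16 g/mol) and then check it against the table's own figures.

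**Step 1: convert the mg/dL limits.** Formula: mmol/L = (mg/dL) / 18.016.

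| mg/dL | Computed mmol/L | Printed mmol/L | Printed ratio | Agrees? |
|---|---|---|---|---|
| 160 | 8.88 | 8.9 | 160/8.9 = 17.98 | yes |
| 250 | 13.88 | 13.9 | 250/13.9 = 17.99 | yes |
| 500 | 27.75 | 27.8 | 500/27.8 = 17.99 | yes |
| 130 | 7.22 | 6.0 | 130/6.0 = 21.67 | no |

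**Step 2: convert back.** 6.0 × 18.016 = 108.1 mg/dL. The gap is 130 − 108 = 22 mg/dL, or 7.2 − 6.0 = 1.2 mmol/L.

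**Step 3: test whether rounding or the choice of factor could explain it.** Suppose each mmol/L figure is rounded to 0.1. The three consistent pairs then bound the factor:

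- 160/8.95 = 17.88 to 160/8.85 = 18.08
- 250/13.95 = 17.92 to 250/13.85 = 18.05
- 500/27.85 = 17.95 to 500/27.75 = 18.02

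All three hold only for a factor between 17.95 and 18.02. Over that range 130 mg/dL is 7.215 to 7.241 mmol/L. Allowing also for rounding of 6.0, the mmol/L limit lies between 5.95 × 17.953 = 106.8 and 6.05 × 18.018 = 109.0 mg/dL. The two limits never meet.

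**Step 4: trace what depends on this boundary.**

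- *Dosing.* Grade 1 calls for no dose change. The boundaries between Grades 1 and 2, 2 and 3, and 3 and 4 agree in both units. Table 6 makes resumption after a Grade 3 event depend on recovery to Grade 2 or lower, which is the 250/13.9 boundary.
- *HbA1c, patients with a history of diabetes.* Sections 7.3, 7.4.2 and 7.5 schedule HbA1c together with fasting plasma glucose, so at those visits it is measured whatever the grade.
- *HbA1c, other patients.* Fasting glucose is not scheduled. Glucose is part of the metabolic profile in Section 7.6.3, which does not call for fasting. For these patients the Grade 1 prompt to check HbA1c arises only if a fasting value is obtained outside the schedule, and in the 108 to 130 mg/dL band it then depends on the unit.
- *Referral.* The 7.0% HbA1c threshold is the same in either unit. Section 6.1.3.3 also has referral triggers that need no glucose grade: above 7% at baseline, or on treatment a rise of 1.5% or a value above 8.0%. What remains unit-dependent is referral of an on-treatment patient whose HbA1c is above 7.0% but meets neither on-treatment trigger.

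**The case against.** The strongest reply is that the slip has almost no practical reach. The synopsis says "This is a multicenter study to be conducted in the United States at approximately 15 sites", and the protocol uses conventional units elsewhere (hemoglobin in g/dL, creatinine in mg/dL). Sites will probably read the mg/dL figure and grade alike. That is a fair assumption and it reduces inconsistency between sites. It does not settle the matter, because the protocol names no controlling unit and uniform use of 130 mg/dL would not show that 130 was the intended limit.

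A reader might infer larger consequences. The documents do not support them:

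- *That HbA1c monitoring as a whole turns on the unit.* It does not, because HbA1c is already scheduled alongside fasting glucose in patients with a history of diabetes.
- *That the safety tables would be distorted.* Section 10.7 summarizes adverse events by CTCAE severity, but Section 11.4.3 has Grade 1 or 2 laboratory values recorded as adverse events only when clinically significant. It is also arguable whether Table 6, an action table citing CTCAE as its source, sets the grade for those summaries. An isolated fasting value in the band would not automatically enter any table.
- *That some eligible diabetic patients start the study with a Grade 1 event.* Exclusion 16 in Section 3.2 admits Type II patients if "they require only oral hypoglycemic agents and fasting blood glucose level" is at most 120, with no unit printed. If that is mg/dL, it is 120/18.016 = 6.7 mmol/L, inside the band. But Section 11.4.6 counts a condition present at the start as an adverse event only if it worsens.
- *That dosing or efficacy is touched.* Grade 1 carries no dose modification, and the response and survival endpoints do not use this limit.

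An error in reading the PDF cannot be excluded from the text alone, but nothing around the figure suggests one.

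**Conclusion.** The contradiction is real and follows from the table's own figures. A band of about 22 mg/dL (1.2 mmol/L) is Grade 1 under one unit and below Grade 1 under the other. The consequence is minor: it is confined to the Grade 1 label, the medication-compliance review, the HbA1c check where none is scheduled, and the narrow group referred solely because of that check. How many patients would fall in the band is not in the documents. Two things rest on assumption: the physical conversion factor, which the table's other limits confirm, and US sites reading mg/dL, which would shrink the practical effect further. The arithmetic is certain; the impact is small. It is worth correcting because the table is operative and the correction is trivial.

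**What to change.** Reconcile the two Grade 1 lower limits in Table 6 to a single value, expressed consistently in mg/dL and mmol/L. Which value applies is for the medical team to decide; this check does not favor either. The sponsor should first compare the printed table with its source to rule out a transcription slip. The cost is one corrected table cell at the next amendment, with no effect on sample size, visit schedule or planned analyses.
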